6.1.2 Timing of Dose Administration

Trial treatment should be administered on Day 1 of each cycle after all procedures/assessments have been completed as detailed on the Trial Flow Chart (Section 7.0). Trial treatment may be administered up to 3 days before or after the scheduled Day 1 of each cycle due to administrative reasons, including patient's desire.

All trial treatments will be administered on an outpatient basis.

MK-3475 will be administered as a 30 minute IV infusion (treatment cycle intervals may be increased due to toxicity as described in Section 5.2.1.2). Sites should make every effort to target infusion timing to be as close to 30 minutes as possible. However, given the variability of infusion pumps from site to site, a window of -5 minutes and +10 minutes is permitted (i.e., infusion time is 30 minutes: -5 min/+10 min).

Merck will provide Pharmacy Manual which contains specific instructions for MK-3475 dose calculation, reconstitution, preparation of the infusion fluid, and administration.

6.2 Concomitant Medications/Vaccinations (allowed & prohibited)

Medications or vaccinations specifically prohibited in the exclusion criteria are not allowed during the ongoing trial. If there is a clinical indication for one of these or other medications or vaccinations specifically prohibited during the trial, discontinuation from trial therapy or vaccination may be required. The investigator should discuss any questions regarding this with the Principal Investigator. The final decision on any supportive therapy or vaccination rests with the investigator. However, the decision to continue the subject on trial therapy or vaccination schedule requires the mutual agreement of the Investigator, and the subject.

6.2.1 Acceptable Concomitant Medications

All treatments that the investigator considers necessary for a subject's welfare may be administered at the discretion of the investigator in keeping with the community standards of medical care. All concomitant medication will be recorded on the case report form (CRF). All concomitant medications at the time of study enrollment and study therapy discontinuation should be recorded.

6.2.2 Prohibited Concomitant Medications

Subjects are prohibited from receiving the following therapies during the Screening and Treatment Phase (including retreatment for post-complete response relapse) of this trial:

- Anti-cancer systemic chemotherapy or biological therapy
- Immunotherapy not specified in this protocol
- Investigational agents other than MK-3475
- Radiation therapy
 - Note: Radiation therapy to a symptomatic solitary lesion or to the brain may be allowed after consultation with the Principal Investigator
- Live vaccines within 30 days prior to the first dose of trial treatment and while participating in the trial. Examples of live vaccines include, but are not limited to, the following: measles, mumps, rubella, chicken pox, yellow fever, rabies, BCG, and typhoid (oral) vaccine. Seasonal influenza vaccines for injection are generally killed virus vaccines and are allowed; however intranasal influenza vaccines (e.g. Flu-Mist®) are live attenuated vaccines, and are not allowed.
- Glucocorticoids for any purpose other than to modulate symptoms from an event of clinical interest of suspected immunologic etiology. The use of physiologic doses of corticosteroids may be approved after consultation with the Principal Investigator.
- **Patients CAN continue on bone modifying agents such as zoledronic acid or denosumab if deemed necessary by the treating physician.**

6.3 Rescue Medications & AE Mangement

6.3.1 Supportive Care Guidelines

Subjects should receive appropriate supportive care measures as deemed necessary by the treating investigator including but not limited to the items outlined below:

- Diarrhea: Subjects should be carefully monitored for signs and symptoms of enterocolitis (such as diarrhea, abdominal pain, blood or mucus in stool, with or without fever) and of bowel perforation (such as peritoneal signs and ileus). In symptomatic subjects, infectious etiologies should be ruled out, and if symptoms are persistent and/or severe, endoscopic evaluation should be considered.
 - In subjects with severe enterocolitis (Grade 3 or greater), MK-3475 will be permanently discontinued and treatment with systemic corticosteroids should be initiated at a dose of 1 to 2 mg/kg/day of prednisone or equivalent. When symptoms improve to Grade 1 or less, corticosteroid taper should be started and continued over at least 1 month. **If the treating physician believes that the patient is deriving clinical benefit from the study drug, then the treating physician after consultation with the Principal Investigator may discuss with the patient regarding continuing therapy with MK-3475**
 - In subjects with moderate enterocolitis (Grade 2), MK-3475 should be withheld and anti-diarrheal treatment should be started. If symptoms are persistent for more than one week, systemic corticosteroids should be initiated (e.g., 0.5 mg/kg/day of prednisone or equivalent). When symptoms improve to Grade 1 or less, corticosteroid taper should be started and continued over at least 1 month. Regarding guidelines for continuing treatment with MK-3475, see Section 5.2.
 - All subjects who experience diarrhea should be advised to drink liberal quantities of clear fluids. If sufficient oral fluid intake is not feasible, fluid and electrolytes should be substituted via IV infusion.
- Nausea/vomiting: Nausea and vomiting should be treated aggressively, and consideration should be given in subsequent cycles to the administration of prophylactic antiemetic therapy according to standard institutional practice. Subjects should be strongly encouraged to maintain liberal oral fluid intake.
- Anti-infectives: Subjects with a documented infectious complication should receive oral or IV antibiotics or other anti-infective agents as considered appropriate by the treating investigator for a given infectious condition, according to standard institutional practice.

- Immune-related adverse events: Please see Section 6.3.1.1 below regarding diagnosis and management of adverse experiences of a potential immunologic etiology.
- Management of Infusion Reactions: Acute infusion reactions (which can include cytokine release syndrome, angioedema, or anaphylaxis) are different from allergic/hypersensitive reactions, although some of the manifestations are common to both AEs. Signs and symptoms usually develop during or shortly after drug infusion and generally resolve completely within 24 hours of completion of infusion. Signs/symptoms may include: Allergic reaction/hypersensitivity (including drug fever); Arthralgia (joint pain); Bronchospasm; Cough; Dizziness; Dyspnea (shortness of breath); Fatigue (asthenia, lethargy, malaise); Headache; Hypertension; Hypotension; Myalgia (muscle pain); Nausea; Pruritis/itching; Rash/desquamation; Rigors/chills; Sweating (diaphoresis); Tachycardia; Tumor pain (onset or exacerbation of tumor pain due to treatment); Urticaria (hives, welts, wheals); Vomiting.

Table 4 below shows treatment guidelines for subjects who experience an infusion reaction associated with administration of MK-3475.

Table 4 Infusion Reaction Treatment Guidelines

NCI CTCAE Grade	Treatment	Premedication at subsequent dosing
Grade 1 Mild reaction; infusion interruption not indicated; intervention not indicated	Increase monitoring of vital signs as medically indicated until the subject is deemed medically stable in the opinion of the investigator.	None
Grade 2 Requires infusion interruption but responds promptly to symptomatic treatment (e.g., antihistamines, NSAIDS, narcotics, IV fluids); prophylactic medications indicated for < =24 hrs	
Stop Infusion and monitor symptoms. Additional appropriate medical therapy may include but is not limited to:
 
 IV fluids Antihistamines NSAIDS Acetaminophen Narcotics 
Increase monitoring of vital signs as medically indicated until the subject is deemed medically stable in the opinion of the investigator. If symptoms resolve within one hour of stopping drug infusion, the infusion may be restarted at 50% of the original infusion rate (e.g. from 100 mL/hr to 50 mL/hr). Otherwise dosing will be held until symptoms resolve and the subject should be premedicated for the next scheduled dose.
 
Subjects who develop Grade 2 toxicity despite adequate premedication should be permanently discontinued from further trial treatment administration.
	
Subject may be premedicated 1.5h (± 30 minutes) prior to infusion of MK-3475 with:
 
Diphenhydramine 50 mg po (or equivalent dose of antihistamine).
 
Acetaminophen 500-1000 mg po (or equivalent dose of antipyretic).

NCI CTCAE Grade	Treatment	Premedication at subsequent dosing

Grades 3 or 4
 
Grade 3: Prolonged (i.e., not rapidly responsive to symptomatic medication and/or brief interruption of infusion); recurrence of symptoms following initial improvement; hospitalization indicated for other clinical sequelae (e.g., renal impairment, pulmonary infiltrates)
 
Grade 4: Life-threatening; pressor or ventilatory support indicated
	
Stop Infusion. Additional appropriate medical therapy may include but is not limited to:
 
 IV fluids Antihistamines NSAIDS Acetaminophen Narcotics Oxygen Pressors Corticosteroids Epinephrine 
Increase monitoring of vital signs as medically indicated until the subject is deemed medically stable in the opinion of the investigator. Hospitalization may be indicated.
 
Subject is permanently discontinued from further trial treatment administration.
	
No subsequent dosing

Appropriate resuscitation equipment should be available in the room and a physician readily available during the period of drug administration. For Further information, please refer to the Common Terminology Criteria for Adverse Events v4.0 (CTCAE) at http://ctep.cancer.gov
		

6.3.1.1 Supportive Care Guidelines for Events of Clinical Interest and Immune-related Adverse Events (irAEs)

Events of clinical interest of a potential immunologic etiology (irECIs) may be defined as an adverse event of unknown etiology, associated with drug exposure and is consistent with an immune phenomenon. irAEs may be predicted based on the nature of the MK-3475 compound, its mechanism of action, and reported experience with immunotherapies that have a similar mechanism of action. Special attention should be paid to AEs that may be suggestive of potential irAEs. An irAE can occur shortly after the first dose or **several months after the last dose of treatment**. Examples of such events include pneumonitis, pancreatitis, thyroid disorders.

If an irAE is suspected, efforts should be made to rule out neoplastic, infectious, metabolic, toxin or other etiologic causes prior to labeling an adverse event as an irAE. Information on possible irAEs is included in the Appendix in Section 15.4. Subjects who develop a Grade 2 or higher irAE should be discussed immediately with the Principal Investigator.

Recommendations to managing irAEs not detailed elsewhere in the protocol are detailed in Table 5.

Table 5. General Approach to Handling irAEs

irAE	Withhold/Discontinue MK-3475?	Supportive Care
Grade 1	No action	Provide symptomatic treatment
Grade 2	May withhold MK-3475	Consider systemic corticosteroids in addition to appropriate symptomatic treatment
Grade 3 and Grade 4	Withhold MK-3475 Discontinue if unable to reduce corticosteroid dose to < 10 mg per day prednisone equivalent within 12 weeks of toxicity	Systemic corticosteroids are indicated in addition to appropriate symptomatic treatment. May utilize 1 to 2 mg/kg prednisone or equivalent per day. Steroid taper should be considered once symptoms improve to Grade 1 or less and tapered over at least 4 weeks.

6.3.1.1.1 Management of Possible immune related Adverse Events (irAEs) (see also Appendix, Section 15.4)

Each of the clinical conditions listed below can have causes other than immune related. Appropriate evaluation to determine the cause of the events is necessary and only after other possible causes have been determined to be less likely should the Principal Investigator be contacted within 72 hours. **Please note if the ECI meets the SAE reporting guidelines then the SAE reporting guidelines should be followed.**

6.3.1.1.1a Diarrhea- All attempts should be made to rule out other causes such as metastatic disease, bacterial or parasitic infection, viral gastroenteritis, or the first manifestation of an inflammatory bowel disease by examination for stool leukocytes, stool cultures, and a Clostridium difficile titer.

Course of Action

Grade 1 diarrhea:

- Treat symptomatically (loperamide, oral hydration, electrolyte substitution and ADA colitis diet).
- Endoscopy is recommended if symptoms persist.

Grade 2 diarrhea (or persistent Grade 1):

- Hold MK-3475.
- GI consultation and endoscopy is recommended to confirm or rule out colitis for Grade 2 diarrhea that persists >1 week or Grade 1-2 diarrhea with rectal bleeding (additional guidelines for the treatment of persistent colitis are provided below).

- Grade 1 events that persist for >1 week or Grade 2 events should be treated with the addition of oral diphenoxylate hydrochloride and atropine sulfate four times daily and budesonide 9 mg daily.
- Grade 2 diarrhea with diffuse ulceration and bleeding seen on endoscopy may require oral steroids with prolonged taper and represent an increased risk for the development of bowel perforation.
- When symptoms improve to Grade 1 or less, steroid taper should be started and continued over no less than 4 weeks.

Grade 3-4 diarrhea (or Grade 2 diarrhea that persist after initial steroid treatment):

- Hold/Discontinue MK-3475.
- Rule out bowel perforation. Imaging with plain films or CT can be useful.
- Consider consultation with Gastroenterologist and confirmation biopsy with endoscopy
- Treat with intravenous steroids (methylprednisolone 125 mg) followed by high dose oral steroids (prednisone 1 to 2 mg/kg once per day or dexamethasone 4 mg every 4 hours) When symptoms improve to Grade 1 or less, steroid taper should be started and continued over no less than 4 weeks. Taper over 6 to 8 weeks in patients with diffuse and severe ulceration and/or bleeding.
- If IV steroids followed by high dose oral steroids does not reduce initial symptoms within 48 to 72 hours, consider treatment with infliximab at 5 mg/kg once every 2 weeks. Discontinue infliximab upon symptom relief and initiate a prolonged steroid taper over 45 to 60 days. If symptoms worsening during steroid reduction, initiate a retapering of steroids starting at a higher dose of 80 or 100 mg followed by a more prolonged taper and administer infliximab. CAUTION: infliximab is contraindicated in patients with bowel perforation or sepsis [12].
- If symptoms persist despite the above treatment a surgical consult should be obtained.

After patient has recovered the treating physician may consider restarting therapy with the study drug after consultation with the Principal Investigator.

6.3.1.1.1b Endocrine Abnormalities

Possible endocrine disorders that could arise include- Adrenal Insufficiency, Hypothyroidism, Hyperthyroidism, Thyroiditis, Hypophysitis, Hypopituitarism.

Course of Action

Grade 1-2 events:

- Monitor thyroid function or other hormonal level tests and serum chemistries more frequently until returned to baseline values.
- If hypophysitis is considered, pituitary gland imaging should be considered (MRIs with gadolinium and selective cuts of the pituitary can show enlargement or heterogeneity and confirm the diagnosis).
- Thyroid hormone and/or steroid replacement therapy should be considered in appropriate patients.

Symptomatic pan-hypopituitarism and any Grade 3-4 events

- Hold/discontinue MK-3475.
- Consider Endocrine consultation.
- Rule out infection and sepsis with appropriate cultures and imaging.
- Treat with an initial dose of methylprednisolone 1 to 2 mg/kg intravenously followed by oral prednisone 1 to 2 mg/kg per day. When symptoms improve to Grade 1 or less, steroid taper should be started and continued over no less than 4 weeks. Replacement of appropriate hormones may be required as the steroid dose is tapered.
- Hypophysitis with clinically significant adrenal insufficiency and hypotension, dehydration, and electrolyte abnormalities (such as hyponatremia and hyperkalemia) constitutes adrenal crisis. Hospitalization and intravenous methylprednisolone should be initiated.

After patient has recovered the treating physician may consider restarting therapy with the study drug after consultation with the Principal Investigator.

6.3.1.1.1c Ocular Events

The following AE term, if considered Grade ≥ 2 , is considered an ECI and should be reported to the Principal Investigator within 72 hours of the event:

- Uveitis

Course of Action for Ocular Events

Grade 1-2 events:

- Evaluation by an ophthalmologist is strongly recommended.
- Treat with topical steroids such as 1% prednisolone acetate suspension and iridocyclitics.
- Discontinue MK-3475 if symptoms persist despite treatment with topical immunosuppressive therapy.

Grade 3-4 events:

- Discontinue MK-3475.
- Treat with systemic corticosteroids such as prednisone at a dose of 1 to 2 mg/kg per day. When symptoms improve to Grade 1 or less, steroid taper should be started and continued over no less than 4 weeks.

After patient has recovered the treating physician may consider restarting therapy with the study drug after consultation with the Principal Investigator.

6.3.1.1.1d Hepatic

The following AE terms, if considered \geq Grade 2, are considered ECIs and should be reported to the Principal Investigator within 72 hours of the event.

Symptoms may include (but not limited to):

- Elevations in: AST >2.5 times upper limit of normal (ULN), ALT >2.5 times ULN, Total bilirubin >1.5 times ULN, Fever, Malaise, Upper quadrant abdominal pain.

Course of Action

Grade 1 events: Monitor liver function tests more frequently until returned to baseline values.

Grade 2 events: Monitor liver function tests more frequently until returned to baseline values.

Grade 3-4 events: Discontinue MK-3475 when AST or ALT >5.0 times ULN and/or total bilirubin >3.0 times ULN

- Consider appropriate consultation and liver biopsy to establish etiology of hepatic injury, if necessary
- Treat with high-dose intravenous glucocorticosteroids for 24 to 48 hours. When symptoms improve to Grade 1 or less, a steroid taper with dexamethasone 4 mg

every 4 hours or prednisone at 1 to 2 mg/kg should be started and continued over no less than 4 weeks.

- If serum transaminase levels do not decrease 48 hours after initiation of systemic steroids, oral mycophenolate mofetil 500 mg every 12 hours may be given. Infliximab is not recommended due to its potential for hepatotoxicity [12].
- Several courses of steroid tapering may be necessary as symptoms may worsen when the steroid dose is decreased.

After patient has recovered the treating physician may consider restarting therapy with the study drug after consultation with the Principal Investigator.

6.3.1.1.1e Renal

The following AEs if \geq Grade 2 are considered ECIs and should be reported to the Sponsor within 24 hours of the event:

- Nephritis
- Nephritis autoimmune
- Renal failure
- Renal failure, Acute

Course of Action

Grade 1 events:

- Mild (Grade 1) irAEs – provide symptomatic treatment.

Grade 2 events:

- Moderate (Grade 2) or Grade 1 irAEs that do not improve with symptomatic treatment – consider withholding MK-3475. Systemic corticosteroids may be indicated.

Grade 3-4 events:

- Clinically significant or severe (\geq Grade 3) irAEs
- Discontinue MK-3475
- Renal consultation with consideration of ultrasound and/or biopsy as appropriate
- Treat with systemic corticosteroids at a dose of 1 to 2 mg/kg prednisone or equivalent once per day.

When symptoms improve to Grade 1 or less, steroid taper should be started and continued over no less than 4 weeks.

Discontinue MK-3475 if unable to reduce corticosteroid dose for irAEs to ≤ 10 mg.

After patient has recovered the treating physician may consider restarting therapy with the study drug after consultation with the Principal Investigator.

6.3.1.1.1f Dermatologic

The following AEs should always be reported as ECIs, regardless of CTCAE grade, and should be reported to the Principal Investigator within 72 hours of the event:

- Dermatitis Exfoliative
- Erythema Multiforme
- Stevens-Johnson Syndrome
- Toxic Epidermal Necrolysis

The following AE terms should only be reported as an ECI if they are considered to be immune related, \geq Grade 3 or result in dose modification or discontinuation:

- Pruritus
- Rash
- Rash generalized
- Rash maculo-papular
- Vitiligo

Course of Action with MK-3475

Grade 1-2 events:

- Symptomatic treatment should be given such as topical glucocorticosteroids (e.g., betamethasone 0.1% cream or hydrocortisone 1%) or urea-containing creams in combination with oral antipruritics (e.g., diphenhydramine HCl or hydroxyzine HCl).
- Treatment with oral steroids is at investigator discretion for Grade 2 events.

Grade 3 events:

- Hold MK-3475.
- Consider Dermatology Consultation and biopsy for confirmation of diagnosis.

- Treatment with oral steroids is recommended, starting with 1 mg/kg prednisone or equivalent once per day or dexamethasone 4 mg four times orally daily. When symptoms improve to Grade 1 or less, steroid taper should be started and continued over no less than 4 weeks.

Grade 4 events:

- Permanently discontinue MK-3475.
- Dermatology consultation and consideration of biopsy and clinical dermatology photograph.
- Initiate steroids at 1 to 2 mg/kg prednisone or equivalent. When symptoms improve to Grade 1 or less, steroid taper should be started and continued over no less than 4 weeks.

6.3.1.1.1g Pneumonitis

Subjects with symptomatic pneumonitis should immediately stop receiving MK-3475 and have an evaluation. The evaluation may include bronchoscopy and pulmonary function tests to rule out other causes such as infection. If the subject is determined to have study drug associated pneumonitis, the suggested treatment plan is detailed in Table 6.

Table 6 Recommended Approach to Handling Pneumonitis

Study drug associated pneumonitis	Withhold/Discontinue MK-3475?	Supportive Care
Grade 1 (asymptomatic)	No action	Intervention not indicated
Grade 2	Withhold MK-3475, may return to treatment if improves to Grade 1 or resolves within 12 weeks	Systemic corticosteroids are indicated. Taper if necessary.
Grade 3 and Grade 4	Discontinue MK-3475	Systemic corticosteroids are indicated. The use of infliximab may be indicated as appropriate. Refer to the Event of Clinical Interest and Immune-related Adverse Event Guidance Document for additional recommendations.

For Grade 2 pneumonitis that improves to \leq Grade 1 within 12 weeks, the following rules should apply:

- First episode of pneumonitis
 - May increase dosing interval by one week in subsequent cycles
- Second episode of pneumonitis – permanently discontinue MK-3475 if upon rechallenge subject develops pneumonitis \geq Grade 2

6.3.1.1.1h Other

The following AEs are considered ECIs and should be reported to the Principal Investigator within 72 hours of the event:

- Autoimmune Neuropathy
- Demyelinating Polyneuropathy
- Guillain-Barre
- Myasthenia Gravis-like Syndrome
- Non-infectious myocarditis
- Non-infectious pericarditis
- Pancreatitis
- Rapid onset of Grade 3 fatigue in the absence of disease progression

Course of Action

- Mild (Grade 1) irAEs – provide symptomatic treatment.
- Moderate (Grade 2) or Grade 1 irAEs that do not improve with symptomatic treatment – consider withholding MK-3475. Systemic corticosteroids may be indicated. Consider biopsy for confirmation of diagnosis.
- Clinically significant or severe (\geq Grade 3) irAEs –discontinue MK-3475 and treat with systemic corticosteroids at a dose of 1 to 2 mg/kg prednisone or equivalent once per day. Report as ECI.

When symptoms improve to Grade 1 or less, steroid taper should be started and continued over no less than 4 weeks.

Discontinue MK-3475 if unable to reduce corticosteroid dose for irAEs to \leq 10 mg. MK-3475 treatment may be restarted and the dose modified as specified in the protocol

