3.5 Pneumonitis

The following AE terms, if considered \geq Grade 2, are considered ECIs and should be reported to the Principal Investigator within 72 hours of the event:

- Pneumonitis
- Interstitial lung disease
- Acute interstitial pneumonitis

The following signs and symptoms may be associated with any of the above diagnoses. The signs and symptoms represent one of the included adverse events, but do not need to be reported as an ECI unless the investigator suspects one of the ECI events listed above.

Symptoms

Symptoms may include (but not limited to):

- Abnormal breath sounds
- Chest pain and/or tightness*
- Dyspnea*
- Dry cough
- Fatigue
- Fever
- Hemoptysis

*If symptoms indicate possible new or worsening cardiac abnormalities additional testing and/or a cardiology consultation should be considered.

Differential Diagnosis

All attempts should be made to rule out other causes such as metastatic disease, bacterial or viral infection.

Course of Action

Grade 1 events: (asymptomatic with radiographic findings only):

- MK-3475 may be continued with close monitoring.
- Radiologic findings should be followed on serial imaging studies.
- Consider pulmonary consultation and/or bronchoscopy if clinically indicated.

Grade 2 events:

- Hold MK-3475 as specified in the protocol.
- Consider pulmonary consultation with bronchoscopy and biopsy/BAL.
- Consider pulmonary function tests.
- Treat with systemic corticosteroids at a dose of 1 to 2 mg/kg/day prednisone or equivalent. When symptoms improve to Grade 1 or less, steroid taper should be started and continued over no less than 4 weeks.
- Treatment with MK-3475 may be resumed if the event improves to grade 0 or 1 within 12 weeks and corticosteroids have been reduced to the equivalent of methylprednisolone 10 mg po daily or less. Repeat chest imaging monthly as clinically indicated.
- Second episode of pneumonitis – discontinue MK-3475 if upon rechallenge the patient develops a second episode of Grade 2 or higher pneumonitis.

Grade 3 and 4 events:

- Permanently Discontinue MK-3475.
- Consider pulmonary function tests with pulmonary consult.
- Bronchoscopy with biopsy and/or BAL is recommended.
- Treat with intravenous steroids (methylprednisolone 125 mg). When symptoms improve to Grade 1 or less, a high dose oral steroid (prednisone 1 to 2 mg/kg once per day or dexamethasone 4 mg every 4 hours) taper should be started and continued over no less than 4 weeks.

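### The protocol gives two conflicting steroid pathways for Grade 2 diarrhoea/enterocolitis and does not say which governs; Grade 2 pneumonitis has a similar mismatch

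*Combined protocol and SAP*

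**What the plan says.** **Section 6.3.1, diarrhoea bullet.** For Grade 2 the first step is: "In subjects with moderate enterocolitis (Grade 2), MK-3475 should be withheld and anti-diarrheal treatment should be started". No steroid is named at that step. Then: "If symptoms are persistent for more than one week, systemic corticosteroids should be initiated (e.g., 0.5 mg/kg/day of prednisone or equivalent". For Grade 3 or greater, "treatment with systemic corticosteroids should be initiated at a dose of 1 to 2 mg/kg/day of prednisone or equivalent".

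**Section 6.3.1.1.1a, with the same wording in Appendix 15.4 section 3.1 (Colitis).** The drug is also held at Grade 2, but the treatment differs: "Grade 1 events that persist for >1 week or Grade 2 events should be treated with the addition of oral diphenoxylate hydrochloride", and the sentence goes on to add budesonide 9 mg daily. Where endoscopy shows diffuse ulceration and bleeding, oral steroids may be required; no dose is given. The next tier is headed "Grade 3-4 diarrhea (or Grade 2 diarrhea that persist after initial steroid treatment", and its regimen begins "Treat with intravenous steroids (methylprednisolone 125 mg) followed by high dose oral steroids". The oral options are prednisone 1 to 2 mg/kg once daily or dexamethasone 4 mg every 4 hours.

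**Grade 2 pneumonitis.** Table 6 in section 6.3.1.1.1g says "Systemic corticosteroids are indicated. Taper if necessary", with no dose. Appendix 15.4 section 3.5 gives prednisone 1 to 2 mg/kg/day or equivalent and says "When symptoms improve to Grade 1 or less, steroid taper should be started and continued over no less than 4 weeks".

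**Links between the texts.** Section 6.3.1 sends the reader to 6.3.1.1 for immune-related events, and 6.3.1.1.1 cross-refers to Appendix 15.4. Neither says that one text overrides another.

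**The concern.** A site with a Grade 2 case can follow either text in good faith and treat the patient differently. The texts cannot easily be separated as covering different conditions. The 6.3.1 bullet is headed as diarrhoea and lists diarrhoea among the signs of enterocolitis. Appendix 15.4 section 3.1 places the diarrhoea regimen under colitis, and enterocolitis is one of its listed terms.

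What is at stake is uniform management of an immune-mediated event at 4 to 5 sites. The protocol itself names immune-mediated events as an important concern with this drug, and it links one Grade 2 presentation to a higher risk of bowel perforation.

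**Working it through.** The plan states no figure to reproduce, and no sample size, power or event count is involved. The check sets the texts side by side and takes ratios of the stated daily doses.

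**Grade 2 diarrhoea/enterocolitis**

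| Stage | Section 6.3.1 | Section 6.3.1.1.1a and Appendix 15.4, 3.1 |
|---|---|---|
| First week | Anti-diarrhoeals; no steroid named | Diphenoxylate/atropine plus budesonide 9 mg daily |
| Trigger for the next step | More than one week of symptoms | Persistence after initial steroid treatment; term not defined, no time limit |
| Next step | Systemic steroid, for example prednisone 0.5 mg/kg/day | If budesonide counts as initial steroid treatment: IV methylprednisolone 125 mg, then prednisone 1-2 mg/kg/day or dexamethasone 4 mg every 4 hours. If it does not count: no systemic steroid is called for on persistence alone; oral steroid may be required with ulceration and bleeding, no dose given |
| Basic taper | At least 1 month | At least 4 weeks |

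1. *First week.* No steroid against budesonide 9 mg daily. No ratio can be formed.
2. *After one week, budesonide counted as initial steroid treatment.* Ratio = (1 to 2 mg/kg/day) / (0.5 mg/kg/day) = 2.0 to 4.0. This does not depend on body weight. At an assumed 70 kg: 0.5 × 70 = 35 mg/day against 70 to 140 mg/day.
3. *The IV step in that branch.* Compared mg for mg with no potency conversion, over an assumed weight range of 50 to 100 kg: 125 / (0.5 × 100) = 2.5 and 125 / (0.5 × 50) = 5.0.
4. *After one week, budesonide not counted.* 6.3.1 starts a systemic steroid. 6.3.1.1.1a does not call for one unless the endoscopic findings apply.
5. *Cumulative exposure.* It cannot be computed, because neither text gives a duration of steroid treatment before the taper.

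**Grade 3-4.** Both texts give prednisone 1 to 2 mg/kg/day, so the oral ratio is 1.0. 6.3.1.1.1a adds the 125 mg IV step and the dexamethasone alternative. Mg for mg, the IV step is 125 / (2 × 100) = 0.6 to 125 / (1 × 50) = 2.5 times one day's oral dose. The basic tapers agree; 6.3.1.1.1a adds 6 to 8 weeks for diffuse and severe ulceration and/or bleeding.

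**Grade 2 pneumonitis.** Table 6 has no dose and leaves the taper to need. Appendix 15.4 section 3.5 has a dose range and a minimum taper of 4 weeks. Table 6 refers the reader to the separate guidance document only in its Grade 3-4 row.

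**The case against.** The strongest reply has four parts.

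*These are guidelines.* Section 6.3.1 leaves supportive care to the treating investigator's judgement, gives 0.5 mg/kg/day only as an example, and names no route. Table 6 is presented as a suggested plan. This stands as far as dose is concerned: the texts guide rather than bind. It does not settle whether and when a Grade 2 patient starts a steroid.

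*The two texts can be read in sequence.* Budesonide could come first, then the 6.3.1 systemic steroid after a week, then the 6.3.1.1.1a escalation if Grade 2 still persists. 6.3.1.1.1a does not bar oral steroids outside ulceration and bleeding. On this reading the 2- to 4-fold gap disappears. It is a possible reading, but the reader has to assemble it, and the difference in the first week remains.

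*There are cross-references and a central check.* Section 6.3.1.1 requires immune-related events of Grade 2 or higher to be discussed immediately with the Principal Investigator. That reduces drift between sites, but it does not rank the texts. Table 5 is limited to events not detailed elsewhere, and so does not rank them either.

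*Few patients are involved.* Section 4.2.1 reports colitis in under 5% of phase I patients and drug-related Grade 3 or higher diarrhoea in under 2%. For 45 patients that is fewer than 45 × 0.05 = 2.25 and 45 × 0.02 = 0.9. The rate of Grade 2 diarrhoea is not given. This stands, and it limits the practical reach of the point.

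A reader might go further and infer that steroid use becomes a site effect that biases the efficacy result. The documents do not support this. Section 4.2.2 offers steroids given during chemotherapy as one of two possible reasons for an ipilimumab finding. This trial is a single-arm PFS study with no planned comparison between sites.

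**Conclusion.** The point holds for Grade 2 diarrhoea/enterocolitis: section 6.3.1 conflicts with 6.3.1.1.1a and its copy in Appendix 15.4 on the start, the agent and the escalation of steroid treatment, with no rule of precedence. The size is a 2- to 4-fold difference in oral daily prednisone dose in one branch only. That branch requires Grade 2 symptoms beyond one week, persistence after initial steroid treatment, budesonide counted as that treatment, and the example dose of 0.5 mg/kg/day being used. A separate mismatch of the same kind holds for Grade 2 pneumonitis.

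Two stronger inferences fail. The documents do not show that the same patient receives several-fold different steroid exposure in general, because the ratio is of daily doses in one branch and cumulative exposure is not computable. Nor is there a several-fold conflict at Grade 3-4, where the oral prednisone range is identical.

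This is an inconsistency in the text and should be corrected for the sake of consistent safety management. No sample size, power or analysis figure depends on it, and no efficacy conclusion is shown to be affected.

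**What to change.** The sponsor's clinical team should reconcile three sets of text into one steroid instruction per event and grade: the diarrhoea bullet in 6.3.1; section 6.3.1.1.1a with Appendix 15.4 section 3.1; and Table 6 in 6.3.1.1.1g with Appendix 15.4 section 3.5. The amendment should:

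- state which section governs;
- define initial steroid treatment, including whether budesonide counts and when persistence is judged;
- delete the duplicate text, so that later edits cannot diverge.

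Which regimen is right is for the clinical team; this review takes no position. The cost is a wording amendment and a memo to sites, with no change to the design, sample size or analysis.
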